9.3. Clinical Monitoring, Data Collection and Data Sharing

9.3.1. Clinical Monitoring Plan

Clinical site monitoring is conducted to ensure that the rights and well-being of trial participants are protected, that the reported trial data are accurate, complete, and verifiable, and that the conduct of the trial is in compliance with the currently approved protocol/amendment(s), with ICH GCP, and with applicable regulatory requirement(s).

Monitoring for this study will be performed by a designated CRO. Details of clinical site monitoring are documented in a Clinical Monitoring Plan (CMP). The CMP describes in detail who will conduct the monitoring, at what frequency monitoring will be done, at what level of detail monitoring will be performed, and the distribution of monitoring reports.

9.3.2. Data Collection

Clinical research data will be collected in a secure electronic web-based clinical data management system (CDMS) through a contract research organization, The Emmes Company LLC (Rockville, MD). Extracted, anonymized data will be sent to the PSRT for safety review and to Protocol Statistician for statistical analysis.

9.3.3. Source Documents

The site will maintain appropriate medical and research records for this trial, in compliance with ICH E6 GCP, regulatory and institutional requirements for the protection of confidentiality of subjects. Source data are all information, original records of clinical findings, observations, or other activities in a clinical trial necessary for the reconstruction and evaluation of the trial. Examples of these original documents and data records include, but are not limited to, medical records, laboratory reports, pharmacy records and other research records maintained for the clinical trial.

9.3.4. Data Sharing

Data generated in this study will be shared as de-identified data in the government-funded public repository, www.ClinicalTrials.gov. Data may be shared prior to publication at approved public presentations or for collaborative development and will be shared at the time of publication or within 1 year of the primary completion date.

9.4 Quality Assurance and Quality Control

The clinical site will perform internal quality management of study conduct, data and biological specimen collection, documentation and completion. The VEC's Quality Management Plan will be used to perform quality management for this trial.

Quality control (QC) procedures will be implemented beginning with the data entry system and QC checks will be run on the database. Any missing data or data anomalies will be communicated to the site for clarification/resolution.

Study monitors will verify that the clinical trial is conducted, and data are generated, and biological specimens are collected, documented (recorded), and reported in compliance with the protocol, ICH GCP, and applicable regulatory requirements. The Principal Investigator will provide direct access to all trial related source data/documents, and reports for the purpose of monitoring and auditing by the sponsor, and inspection by local and regulatory authorities.

9.5. Language

All written information and other material to be used by subjects and investigative staff must use vocabulary and language that are clearly understood.

9.6. Policy Regarding Research-Related Injuries

The NIH CC will provide short-term medical care for any injury resulting from participation in this research. In general, the National Institutes of Health, the NIH CC, or the U.S. Federal Government will provide no long-term medical care or financial compensation for research-related injuries.

APPENDIX I: SCHEDULE OF EVALUATIONS

Schedule 1: IV Group 1 (5 mg/kg), 3 (20 mg/kg), and 4 (40 mg/kg)																		
Visit Number	01	01R	02	02A	02B	02C	02D	02E	02F	03	04	05	06	07	08	11	12	13
Time After Infusion			Pre	EOI	1hr	2hr	4hr	24hr	48hr	Wk1	Wk2	Wk3	Wk4	Wk8	Wk12	Wk16	Wk20	Wk24
¹ Day of Study	-56 to -1	-42 to 0	D0	D0	D0	D0	D1	D2	D7	D14	D21	D28	D56	D84	D112	D140	D168	
Clinical	Tube*	Screen	Enroll	Day of Administration														
VRC 500 Screening Consent		X																
VRC 615 AoU; Consent			X															
² Physical examination		X	X	X					X	X	X	X	X	X	X	X	X	
Complete medical history at screen; then interim med hx		X	X	X					X	X	X	X	X	X	X	X	X	
³ VRC01.23LS Administration				X														
Begin 7-day Diary Card				X														
CBC / differential	EDTA	3		3					3	3	3	3	3	3	3			
ALT, creatinine	GLT	4		4					4	4	4	4	4	4	4			
CMP: Total bili, BUN, albumin, protein, calcium, Na, K, Cl, CO ₂ , glucose, AST, ALP	GLT	X		X							X							
⁴ Pregnancy Test: urine or serum		X	X	X							X				X		X	
⁴ Pregnancy Prevention Counseling		X	X	X							X				X		X	
HIV Ab/Ag combo test	EDTA	3								3								
HIV Risk-Reduction Counseling		X		X						X								
Research Samples																		
PK	SST			4	4	4	4	4	4	4	4	4	4	4	4	4	4	
PBMCs	EDTA			20					20									
Serum	SST			24						8	8	8	8	8	8	8	8	
Daily Volume (mL)		10	0	55	4	4	4	4	31	12	22	19	12	19	12	19	12	
Cumulative Volume (mL)		10	10	65	69	73	77	81	112	124	146	165	177	196	207	227	239	
																	263	

Visit windows: Schedule visits 02A through 13 with respect to day 0:

Visit A (+10 min); Visits B and C (\pm 10 min); Visit D (+2 hrs); Visits E, F (\pm 6 hrs); Visits 03, 04, 05, 06 (\pm 2 days), and Visits 07, 08, 11, 12, 13 (\pm 7 days).

Not applicable to Schedule 1: Visits 02G, 09, 10

*Tube types and blood volumes are shown to meet current institutional requirements and projected blood volumes. Different tubes for clinical evaluations may be used to meet site requirements. Different volumes and tubes may be used for research blood samples when tubes as shown are not available, or as otherwise instructed by the IND Sponsor. Collected blood volumes will stay within the NIH CC blood draw limits for each subject.

¹Day 0=day of first product administration. Day 0 is preferably scheduled within 14 days after enrollment but may be scheduled up to 42 days after enrollment to allow for the possibility of study pauses or scheduling difficulty with the approval of the PI. Day 0 evaluations prior to product administration are the baseline for assessing subsequent AEs.

(Footnotes continue to next page)

² Screening includes physical exam with vital signs (blood pressure, temperature, pulse, respiratory rate), height and weight. At other visits, if medically indicated, perform a targeted exam. Otherwise only vital signs are required, except at Visit 02 when the current weight is also obtained to use for ordering the study product, dosed based on “mg/kg.”

³ The PK blood draw “visits,” defined by hours after an infusion, are relative to the exact time of the end of infusion (EOI). The exact start and end times of product administration and the time of PK blood draw(s) are recorded to ensure accurate PK analysis. In all IV groups, subjects will be observed in clinic for at least 2 hours following completion of product administration.

⁴ Pregnancy test results must be negative for women of reproductive potential before each product administration. Complete a Pregnancy Prevention Form when pregnancy test is given.

Schedule 2: SC Group 2 (5 mg/kg)																
Visit Number	01	01R	02	02A	02E	02F	02G	03	04	05	06	07	08	11	12	13
Time After Infusion			Pre	EOI	24hr	48hr	72hr	Wk1	Wk2	Wk3	Wk4	Wk8	Wk12	Wk16	Wk20	Wk24
¹ Day of Study	-56 to -1	-42 to 0	D0	D0	D1	D2	D3	D7	D14	D21	D28	D56	D84	D112	D140	D168
Clinical	Tube*	Screen	Enroll	Day of Injection												
VRC 500 Screening Consent		X														
VRC 615 AoU; Consent			X													
² Physical examination		X	X	X	X	X	X	X	X	X	X	X	X	X	X	X
Complete medical history at screen; then interim med hx		X	X	X		X	X	X	X	X	X	X	X	X	X	X
³ VRC01.23LS Administration				X												
Begin 7-day Diary Card				X												
CBC / differential	EDTA	3		3		3			3	3		3		3		
ALT, creatinine	GLT	4		4		4			4	4		4		4		
CMP: Total bili, BUN, albumin, protein, calcium, Na, K, Cl, CO ₂ , glucose, AST, ALP	GLT	X		X						X						
⁴ Pregnancy test: urine or serum		X	X	X						X				X		X
⁴ Pregnancy Prevention Counseling		X	X	X						X				X		X
HIV Ab/Ag combo test	EDTA	3							3							
HIV Risk-Reduction Counseling		X		X					X							
Research Samples																
PK	SST			4		4	4	4	4	4	4	4	4	4	4	4
PBMCs	EDTA			20		20										
Serum	SST			24			8	8	8	8	8	8	8	8	8	8
Daily Volume (mL)		10	0	55	0	31	12	12	22	19	12	19	12	19	12	12
Cumulative Volume (mL)		10	10	65	65	96	108	120	142	161	173	192	204	223	235	247
																259

Visit windows: Schedule visits 02A through 13 with respect to day 0:

Visit A (+10 min); Visits E, F, G (± 6 hrs.); Visits 03, 04, 05, 06 (± 2 days); Visits 07, 08, 11, 12, 13 (±7 days).

Not applicable to Schedule 2: Visits 02B, 02C, 02D, 09, 10

* Tube types and blood volumes are shown to meet current institutional requirements and projected blood volumes. Different tubes for clinical evaluations may be used to meet site requirements. Different volumes and tubes may be used for research blood samples when tubes as shown are not available, or as otherwise instructed by the IND Sponsor. Collected blood volumes will stay within the NIH CC blood draw limits for each subject.

¹ Day 0=day of first product administration. Day 0 is preferably scheduled within 14 days after enrollment but may be scheduled up to 42 days after enrollment to allow for the possibility of study pauses or scheduling difficulty with the approval of the PI. Day 0 evaluations prior to product administration are the baseline for assessing subsequent AEs.

(Footnotes continue to next page)

² Screening includes physical exam with vital signs (blood pressure, temperature, pulse, respiratory rate), height and weight. At other visits, if medically indicated, perform a targeted exam. Otherwise only vital signs are required, except at Visit 02 when the current weight is also obtained to use for ordering the study product, dosed based on “mg/kg.”

³ The PK blood draw “visits,” defined by hours after an injection, are relative to the exact time of the end of injection (EOI). The exact start and end times of product administration and the time of PK blood draw(s) are recorded to ensure accurate PK analysis. In all SC groups, subjects will be observed for at least 1 hour after product administration.

⁴ Pregnancy test results must be negative for women of reproductive potential before each product administration. Complete a Pregnancy Prevention Form when pregnancy test is given.

		Schedule 3: SC Group 5 (5 mg/kg by repeat dosing)																					
Visit Number		01	01R	02	02A	02E	02F	02G	03	04	06	07	08	08A	08E	08G	09	10	11	12	13	13A	13E
Time After Infusion				Pre D0	EOI D0	24hr	48hr	72hr	1wk	Wk2	Wk4	Wk8	Pre Wk12	EOI Wk12	24hr	72hr	Wk13	Wk14	Wk16	Wk20	Pre Wk24	EOI Wk24	24hr
¹Day of Study		-56 to -1	-42 to 0	D0	D0	D1	D2	D3	D7	D14	D28	D56	D84	D84	D85	D87	D91	D98	D112	D140	D168	D168	D169
Clinical	Tube*	Screen	Enroll	Day of injection										Day of injection						Day of injection			
VRC 500 Screening Consent		X																					
VRC 615 AoU; Consent			X																				
²Physical examination		X	X	X	X	X	X	X	X	X	X	X	X			X	X	X	X	X	X		
Complete med history at screen; then interim med hx		X	X	X		X	X	X	X	X	X	X	X			X	X	X	X	X	X		
³VRC01.23LS Administration				X										X							X		
Begin 7-day Diary Card				X										X							X		
Phone contact; clinic visit if indicated															X							X	
CBC / differential	EDTA	3		3		3			3	3	3		3			3	3	3	3	3	3		
ALT, creatinine	GLT	4		4		4			4	4	4		4			4	4	4	4	4	4		
CMP: Total bili, BUN, albumin, protein, calcium, Na, K, Cl, CO ₂ , glucose, AST, ALP	GLT	X		X					X			X					X				X		
⁴Pregnancy Test: urine or serum		X	X	X					X			X					X			X			
⁴Pregnancy Prevention Counseling		X	X	X					X			X					X			X			
HIV Ab/Ag combo test	EDTA	3							3								3						
HIV Risk-Reduction Counseling		X		X					X			X				X				X			
Research Samples																							
PK	SST			4		4	4	4	4	4	4	4	4			4	4	4	4	4			
PBMCs	EDTA			20		20																	
Serum	SST			24		8	8	8	8	8	8	8	8			8	8	8	8	8			
Daily Volume (mL)		10	0	55	0	31	12	12	22	19	19	12	19	0	0	19	22	19	19	12	19	0	
Cumulative Volume (mL)		10	10	65	65	96	108	120	142	161	180	192	211	211	211	230	252	271	290	302	321	321	

Visit windows: Schedule visits 02A through 08 with respect to day 0; visits 08A through 13 with respect to visit 08; visits 13A through 21 with respect to visit 13:

Visit A (+10 min); Visits 02E, 02F, 02G, 08G (± 6 hrs.); Visits 08E, 13E (+ 1 day); Visits 03, 04, 09, 10 (± 2 days); Visits 06, 07, 08, 11, 12, 13 (± 7 days, with not less than 21 days between injections).

Not applicable to Schedule 3: Visits B, C, D, 05

*Tube types and blood volumes are shown to meet current institutional requirements and projected blood volumes. Different tubes for clinical evaluations may be used to meet site requirements. Different volumes and tubes may be used for research blood samples when tubes as shown are not available, or as otherwise instructed by the IND Sponsor. Collected blood volumes will stay within the NIH CC blood draw limits for each subject.

¹Day 0=day of first product administration. Day 0 is preferably scheduled within 14 days after enrollment but may be scheduled up to 42 days after enrollment to allow for the possibility of study pauses or scheduling difficulty with the approval of the PI. Day 0 evaluations prior to product administration are the baseline for assessing subsequent AEs. *(Footnotes continue to next page)*

² Screening includes physical exam with vital signs (blood pressure, temperature, pulse, respiratory rate), height and weight. At other visits, if medically indicated, perform a targeted exam. Otherwise only vital signs are required, except at all product administration visits (02, 08, 13) when the current weight is also obtained to use for ordering the study product, dosed based on “mg/kg.”

³ The PK blood draw “visits,” defined by hours after an injection, are relative to the exact time of the end of injection (EOI). The exact start and end times of product administration and the time of PK blood draw(s) are recorded to ensure accurate PK analysis. In all SC groups, subjects will be observed for at least 1 hour after product administration.

⁴ Pregnancy test results must be negative before each study product administration. Complete a Pregnancy Prevention Form when pregnancy test is given.

*The study schedule for subjects who discontinue product administration will be modified as follows:

- Subjects who receive only one product administration will follow Schedule 3 through Visit 07, and then move to Schedule 5.
- Subjects who receive two product administrations will follow Schedule 3 through Visit 12 and then move to Schedule 5.

Schedule 3 (continued): SC Group 5 (5 mg/kg by repeat dosing)										
	Visit Number*	13G	14	15	16	17	18	19	20	21
	Time After Infusion	72 hr	Wk25	Wk26	Wk28	Wk32	Wk36	Wk40	Wk44	Wk48
	Day of Study	D171	D175	D182	D196	D224	D252	D280	D308	D336
Clinical	Tube[^]									
Physical examination if medically indicated, otherwise only vitals		X	X	X	X	X	X	X	X	
Interim medical history		X	X	X	X	X	X	X	X	
CBC / differential	EDTA	3	3	3	3					
ALT, creatinine	GLT	4	4	4	4					
CMP: Total bili, BUN, albumin, protein, calcium, Na, K, Cl, CO ₂ , glucose, AST, ALP	GLT			X						
¹ Pregnancy test: urine or serum				X			X		X	
¹ Pregnancy Prevention Counseling				X			X		X	
HIV Ab/Ag combo test	EDTA		3							
HIV risk-reduction counseling			X							
Research Samples										
PK samples	SST	4	4	4	4	4	4	4	4	
Serum	SST	8	8	8	8	8	8	8	8	
Daily Volume (mL)		19	22	19	19	19	12	12	12	
Cumulative Volume (mL)		340	362	381	400	412	424	436	448	
									460	

Visit windows: Schedule visits 13G through 21 with respect to visit 13.

Visit 13G (\pm 6 hrs), Visits 14-17 (\pm 2 days), and Visits 18-21 (\pm 7 days).

¹ Complete a Pregnancy Prevention Form when pregnancy test is given.

*The study schedule for subjects who discontinue product administration will be modified as follows:

- Subjects who have only received one product administration will follow Schedule 3 through Visit 07, and then move to Schedule 5.
- Subjects who have received two product administrations will follow Schedule 3 through Visit 12 and then move to Schedule 5.

Schedule 4: IV Group 6 (20 mg/kg by repeat dosing)																										
Visit Number		01	01R	02	02A	02B	02C	02D	02E	02F	03	04	06	07	08	08A	08B	08E	08F	09	10	11	12	13	13A	13B
Time After Infusion				Pre D0	EOI D0	1hr	2hr	4hr	24hr	48h	Wk1	Wk2	Wk4	Wk8	Pre Wk12	EOI Wk12	1hr	24hr	48hr	Wk13	Wk14	Wk16	Wk20	Pre Wk24	EOI Wk24	1hr
¹Day of Study		-56 to -1	-42 to 0	D0	D0	D0	D0	D0	D1	D2	D7	D14	D28	D56	D84	D84	D84	D85	D86	D91	D98	D112	D140	D168	D168	D168
Clinical	Tube*	Screen	Enroll	Day of infusion												Day of infusion								Day of infusion		
VRC 500 Screening Consent		X																								
VRC 615 AoU; Consent			X																							
²Physical examination		X	X	X	X					X	X	X	X	X	X	X	X	X	X	X	X	X	X	X	X	
Complete med history at screen; then interim med hx		X	X	X						X	X	X	X	X	X					X	X	X	X	X	X	
³VRC01.23LS Administration				X												X									X	
Begin 7-day Diary Card				X											X										X	
Phone contact; clinic visit if indicated																			X							
CBC / differential	EDTA	3	3						3		3	3	3		3				3	3	3	3	3	3	3	
ALT, creatinine	GLT	4	4						4		4	4	4		4				4	4	4	4	4	4	4	
CMP: Total bili, BUN, albumin, protein, calcium, Na, K, Cl, CO ₂ , glucose, AST, ALP	GLT	X		X							X				X					X				X		
⁴Pregnancy Test: urine or serum		X	X	X							X			X							X			X		
⁴Pregnancy Prevention Counseling			X	X	X						X			X						X			X		X	
HIV Ab/Ag combo test	EDTA	3									3									3						
HIV Risk-Reduction Counseling		X		X							X			X						X				X		
Research Samples																										
PK	SST			4	4	4	4	4	4	4										4	4	4	4	4	4	
PBMCs	EDTA			20						20																
Serum	SST			24							8	8	8	8	8	8				8	8	8	8	8	8	
Daily Volume (mL)		10	0	55	4	4	4	4	31	12	22	19	19	12	19	4	4	0	19	22	19	19	12	19	4	
Cumulative Volume (mL)		10	10	65	69	73	77	81	112	124	146	165	184	196	215	219	223	223	242	264	283	302	314	333	337	

Visit windows: Schedule visits 02A through 08 with respect to Day 0; visits 08A through 13 with respect to Visit 08.

Visits A (+10 min); Visits B and C (±10 min); Visit D (+2 hrs.); Visits 02E, 02F (± 6 hrs.); Visit 08E (+1 day), Visit 08F (+ 2 days), Visits 03, 04, 09, 10 (± 2 days); Visits 06, 07, 08, 11, 12, 13 (±7 days, with not less than 21 days between infusions).

Not applicable to Schedule 4: Visit G, 05, 08C, 08D, 08G, 13B, 13C, 13D

*Tube types and blood volumes are shown to meet current institutional requirements and projected blood volumes. Different tubes for clinical evaluations may be used to meet site requirements. Different volumes and tubes may be used for research blood samples when tubes as shown are not available, or as otherwise instructed by the IND Sponsor. Collected blood volumes will stay within the NIH CC blood draw limits for each subject. (Footnotes continue to next page)

¹ Day 0=day of first product administration. Day 0 is preferably scheduled within 14 days after enrollment but may be scheduled up to 42 days after enrollment to allow for the possibility of study pauses or scheduling difficulty with the approval of the PI. Day 0 evaluations prior to product administration are the baseline for assessing subsequent AEs.

² Screening includes physical exam with vital signs (blood pressure, temperature, pulse, respiratory rate), height and weight. At other visits, if medically indicated, perform a targeted exam. Otherwise only vital signs are required, except at all product administration visits (02, 08, 13) when the current weight is also obtained to use for ordering the study product, dosed based on “mg/kg.”

³ The PK blood draw “visits,” defined by hours after an infusion, are relative to the exact time of the end of infusion. Exact start and end times of product administration and the time of PK blood draw(s) are recorded to ensure accurate PK analysis. In all IV groups, subjects will be observed for at least 2 hours after the product administration.

⁴ Pregnancy test results must be negative for women of reproductive potential before each product administration. Complete a Pregnancy Prevention Form when pregnancy test given.

**The study schedule for subjects who discontinue product administration will be modified as follows:

- Subjects who receive only one product administration will follow Schedule 4 through Visit 07, and then move to Schedule 5.
- Subjects who receive two product administrations will follow Schedule 4 through Visit 12 and then move to Schedule 5.

Schedule 4 (continued): IV Group 6 (20 mg/kg by repeat dosing)											
Visit Number*		13E	13F	14	15	16	17	18	19	20	21
Time After Infusion		24hr	48hr	Wk25	Wk26	Wk28	Wk32	Wk36	Wk40	Wk44	Wk48
Day of Study		D169	D170	D175	D182	D196	D224	D252	D280	D308	D336
Clinical	Tube										
Physical examination if medically indicated, otherwise only vitals			X	X	X	X	X	X	X	X	X
Interim medical history			X	X	X	X	X	X	X	X	X
Phone contact; clinic visit if indicated		X									
CBC / differential	EDTA		3	3	3	3					
ALT, creatinine	GLT		4	4	4	4					
CMP: Total bili, BUN, albumin, protein, calcium, Na, K, Cl, CO2, glucose, AST, ALP	GLT				X						
Pregnancy Test: urine or serum					X			X			X
Pregnancy Prevention Counseling when pregnancy test given					X			X			X
HIV Ab/Ag combo test	EDTA			3							
HIV Risk-Reduction Counseling				X							
Research Samples											
PK	SST		4	4	4	4	4	4	4	4	4
Serum	SST		8	8	8	8	8	8	8	8	8
Daily Volume (mL)		0	19	22	19	19	12	12	12	12	12
Cumulative Volume (mL)		341	360	382	401	420	432	444	456	468	480

Visit windows: Schedule visits 13E through 21 with respect to visit 13.

Visit 13E (+1 day); Visit 13F (+2 days), Visits 14-17 (± 2 days), and Visits 18-21 (± 7 days).

* The study schedule study schedule for subjects who discontinue product administration will be modified as follows:

- Subjects who receive only one product administration will follow Schedule 4 through Visit 7, and then move to Schedule 5.
- Subjects who receive two product administrations will follow Schedule 4 through Visit 12 and then move to Schedule 5.

Schedule 5: For Subjects in Groups 5 and 6 Discontinued from Further Product Administration(s)									
		Visit Number	08	11	12	13	16	17	18
		Time After Infusion	Wk12	Wk16	Wk20	Wk24	Wk28	Wk32	Wk36
		Day of Study	D84	D112	D140	D168	D196	D224	D252
Clinical	Tube*								
Physical examination if medically indicated, otherwise only vitals			X	X	X	X	X	X	X
Interim medical history			X	X	X	X	X	X	X
Pregnancy Test: urine or serum				X		X			X
Pregnancy Prevention Counseling when pregnancy test given				X		X			X
Research Samples									
PK	SST	4	4	4	4	4	4	4	4
Serum	SST	8	8	8	8	8	8	8	8
Daily Volume (mL)			12	12	12	12	12	12	12
If starting at Visit 8	Cumulative Volume (mL), Group 5		211	223	235	247			
	Cumulative Volume (mL), Group 6		215	227	239	251			
If starting at Visit 13	Cumulative Volume (mL), Group 5					321	333	345	357
	Cumulative Volume (mL), Group 6					333	345	357	369

Visit windows: ± 7 days for all visits shown.

*Tube types and blood volumes are shown to meet current institutional requirements and projected blood volumes. Different tubes for clinical evaluations may be used to meet site requirements. Different volumes and tubes may be used for research blood samples when tubes as shown are not available, or as otherwise instructed by the IND Sponsor. Collected blood volumes will stay within the NIH CC blood draw limits for each subject.

Group 5 or 6 subjects who do not receive the 2nd or 3rd product administrations will continue participation under this modified schedule:

- If only one product administration received, subjects will follow their originally assigned study schedule through Visit 7 and then move to Schedule 5 for Visits 8-13. Their final study visit will be Visit 13.
- If two product administrations received, subjects will follow their originally assigned study schedule through Visit 12 and then move to Schedule 5 for Visits 13-18. Their final study visit will be Visit 18.

**APPENDIX II: ASSESSMENT OF RELATIONSHIP TO STUDY PRODUCT AND TABLE
FOR GRADING SEVERITY OF ADVERSE EVENTS**

Assessment of Causality Relationship of an Adverse Event to Study Product:

The relationship between an adverse event (AE) and the product will be assessed by the investigator on the basis of his or her clinical judgment and the definitions below.

- **Definitely Related.** The AE and administration of study product are related in time, and a direct association can be demonstrated.
- **Probably Related.** The AE and administration of study product are reasonably related in time, and the AE is more likely explained by study product than other causes.
- **Possibly Related.** The AE and administration of study product are reasonably related in time, but the AE can be explained equally well by causes other than study product.
- **Not Related.** There is not a reasonable possibility that the AE is related to the study product.

For purposes of preparing data reports in which AE attributions are limited to “**Related**” or “**Not Related**”, in this protocol, the “Definitely, Probably and Possibly” attributions will be mapped to the “**Related**” category. The definitions that apply when these two categories alone are used are as follows:

- **Related** – There is a reasonable possibility that the AE may be related to the study product.
- **Not Related** – There is not a reasonable possibility that the AE is related to the study product.

Table for Grading Severity of Adverse Events:

For consistency with other studies of VRC mAb products, the U.S. Department of Health and Human Services, National Institutes of Health, National Institute of Allergy and Infectious Diseases, Division of AIDS. DAIDS Table for Grading the Severity of Adult and Pediatric Adverse Events, Corrected Version 2.1. [July 2017]. Available from:

[https://rsc.tech-res.com/docs/default-source/safety/division-of-aids-\(daids\)-table-for-grading-the-severity-of-adult-and-pediatric-adverse-events-corrected-v-2-1.pdf](https://rsc.tech-res.com/docs/default-source/safety/division-of-aids-(daids)-table-for-grading-the-severity-of-adult-and-pediatric-adverse-events-corrected-v-2-1.pdf)

The table will be used as posted at the link above with the following exemptions:

- Weight loss will be recorded as an adverse event only if it is considered deleterious to the participant’s health.
- For severity grading of the solicited bruising parameter at the product administration site, the definitions based on size of the largest diameter and listed for the “Injection Site Erythema or Redness” will be used. The severity grade definition for “Bruising” provided under the Dermatologic Clinical Conditions will be used only for unsolicited adverse events involving bruising at other body locations.
- Creatinine changes will be graded on the basis of the upper limit of normal provided by the grading table and not change from baseline.
- Creatinine clearance changes will be graded according to mL/min provided by the grading table and not change from baseline.
- Subclinical CMP results for sodium, potassium, chloride, bicarbonate, BUN, and glucose will not be considered an AE unless grade 2 or greater.

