5. SAFETY AND ADVERSE EVENTS

5.1. Adverse Events

An adverse event (AE) is any untoward medical occurrence associated with the use of a drug in humans, whether or not considered drug related.

- Solicited AEs (i.e., reactogenicity parameters as defined in [4.3.6](#)) will be recorded without attribution assessments by the subject on paper or electronic diary for 7 days after each product administration.
- Unsolicited AEs will be recorded in the study database with attribution assessments from product administration through the Day 28 post-product administration visit.
- SAEs (as detailed in [5.2](#)) and new chronic medical conditions will be recorded as AEs through the last expected study visit or contact.

[Appendix II](#) describes how the relationship between an AE and the study product will be assessed. Also available in [Appendix II](#) is the link to the DAIDS Table for Grading the Severity of Adult and Pediatric Adverse Events, Corrected Version 2.1 [July 2017], which will be used to determine the severity grades of AEs in this protocol with several modifications as noted.

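### Unsolicited AE recording ends at the Day 28 visit, which may fall on Day 21 after doses 1 and 2 in Groups 5 and 6, so late non-serious events can go unrecorded

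*Combined protocol and SAP*

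**What the plan says.** Section 5.1 sets three recording periods. Solicited events are kept in a diary for 7 days after each administration. Unsolicited AEs are recorded "from product administration through the Day 28 post-product administration visit". SAEs and new chronic conditions "will be recorded as AEs through the last expected study visit or contact".

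The windows for the Day 28 visit are in Appendix I:

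- Schedule 2 (Group 2): "Visits 03, 04, 05, 06 (± 2 days". Schedule 1 (Groups 1, 3 and 4) gives Visit 06 the same ±2 days.
- Schedule 3 (Group 5): "Visits 06, 07, 08, 11, 12, 13 (± 7 days, with not less than 21 days between injections". Visit 11 is timed from the second dose: "visits 08A through 13 with respect to visit 08".
- Schedule 4 (Group 6): "Visits 06, 07, 08, 11, 12, 13 (±7 days, with not less than 21 days between infusions".
- Schedule 4 continued: "Visits 14-17 (± 2 days), and Visits 18-21 (± 7 days". Schedule 3 continued gives the same windows. Visit 16 is therefore ±2 days.

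Section 6.3.3 summarises unsolicited AEs as the number and percentage of subjects in each of the six groups, counting a subject once per event. It gives no person-time or per-dose denominator. Solicited AEs, by contrast, are summarised for each administration. The unsolicited AE listing includes onset date and onset study day.

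**The concern.** One milestone, the Day 28 safety visit, has two different windows across groups, and two across doses within the same Group 5 or 6 subject. The documents give no reason for this. Because Section 5.1 ends recording at the visit, a scheduling allowance also becomes a rule about which AEs must enter the database.

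If Visit 06 or Visit 11 takes place on Day 21, a non-serious, non-chronic event starting on Day 24 falls outside required recording. The same event in Groups 1 to 4, or after dose 3, would be inside. Safety is the primary objective. The pause rule in Section 4.7 also counts related Grade 3 or higher AEs whether or not they are serious, so the events at risk are not all trivial. With 5 subjects in a group, one subject is 20 percentage points in the table.

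**Working it through.** **1. The plan's own figures.** Section 6.2.2 gives event probabilities by group size. At a true rate of 0.20, Table 4 is reproduced: 1 − 0.8³ = 0.488 for n=3 and 1 − 0.8⁵ = 0.672 for n=5. These figures carry no observation time, and no length of AE capture is stated elsewhere, so it has to be derived from the schedules.

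**2. Permitted capture per dose.** Capture is the nominal day of the visit minus the day of the dose, plus or minus the window.

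| Groups | Dose | Visit | Nominal days | Window | Capture (days) |
|---|---|---|---|---|---|
| 1–4 | single | 06 | 28 − 0 = 28 | ±2 | 26–30 |
| 5–6 | 1 | 06 | 28 − 0 = 28 | ±7 | 21–35 |
| 5–6 | 2 | 11 | 112 − 84 = 28 | ±7 | 21–35 |
| 5–6 | 3 | 16 | 196 − 168 = 28 | ±2 | 26–30 |

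**3. Largest shortfall against 28 days.** For doses 1 and 2 in Groups 5–6 it is 28 − 21 = 7 days (7/28 = 25%). Elsewhere it is 28 − 26 = 2 days (2/28 = 7%).

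**4. Total capture per subject.**

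- Groups 5–6: minimum 21 + 21 + 26 = 68 days, nominal 3 × 28 = 84, maximum 35 + 35 + 30 = 100.
- Groups 1–4: 26, 28 and 30 days.
- Groups 5–6 with ±2 days at every dose: 3 × 26 = 78 to 3 × 30 = 90 days, still about three times the single-dose groups.

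**5. Illustrative size.** The documents give no AE rate. Assume a constant hazard and a 28-day risk p between 0.05 and 0.40. The risk over d days is 1 − (1 − p)^(d/28).

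| p | 21 d | 26 d | 28 d | 30 d | 35 d | 84 d |
|---|---|---|---|---|---|---|
| 0.05 | 0.038 | 0.047 | 0.050 | 0.053 | 0.062 | 0.143 |
| 0.10 | 0.076 | 0.093 | 0.100 | 0.107 | 0.123 | 0.271 |
| 0.20 | 0.154 | 0.187 | 0.200 | 0.213 | 0.243 | 0.488 |
| 0.40 | 0.318 | 0.378 | 0.400 | 0.421 | 0.472 | 0.784 |

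Moving one dose's visit from Day 28 to Day 21 lowers the risk by 0.050 − 0.038 = 0.012 to 0.400 − 0.318 = 0.082, about 1 to 8 percentage points. Three doses against one raise it by 0.143 − 0.050 = 0.093 to 0.784 − 0.400 = 0.384, about 9 to 38 points. At p = 0.20 the expected number of subjects with an event among 5, for one dose, is 0.77 at 21 days, 1.00 at 28 days and 1.22 at 35 days.

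**6. Is there a direction?** Suppose visits are spread evenly over their window and the rate is 0.5 AEs per 28 days. The average chance of at least one AE is then 39.2% with ±7 days and 39.3% with ±2 days. The gap is about 0.05 points at 0.25 AEs per 28 days and 0.35 points at 1.0.

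**The case against.** A reader might infer that the by-group AE percentages are biased by window length, so that part of any difference between single and repeat dosing reflects the schedule. The documents do not support that. Both windows are symmetric about Day 28, and step 6 shows that averages barely move unless visits in Groups 5–6 drift consistently early or late, which nothing in the documents suggests. The ratio 35/21 = 1.67 compares the earliest and latest permitted visits of two subjects in the same group; it is not a contrast between groups. The unsolicited AE analysis is descriptive, with no between-group test and no planned per-dose summary. At n=5 the plan's own exact interval for 1/5 is 0.005 to 0.716 (Table 5), which dwarfs any window effect.

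The plan also limits the damage. SAEs and new chronic conditions are followed to the last visit, and solicited events have a fixed 7-day period. Section 4.3.6 has clinicians assessing changes in symptoms throughout the study, so a clinician may still learn of a late event. Sections 1.3.2 and 8.2.1 describe typical antibody reactions as early, so non-serious events in the fourth week are more likely to be background, and a constant hazard probably overstates the product-related part.

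All of this stands, and it is why the point is small. It does not answer the early-visit case: required recording can stop up to 7 days short of Day 28, and onset dates cannot restore an event that was never recorded.

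**Conclusion.** The discrepancy is real but minor. Capture per dose may run 21–35 days after doses 1 and 2 in Groups 5–6 and 26–30 days otherwise. This adds spread between subjects and doses; it does not create a directional difference between groups. The inequality between groups that is certain comes from dose number: 84 against 28 nominal days, reported with no per-dose or person-time denominator. Aligning the windows would not remove it.

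The practical harm is the possible loss of non-serious, non-chronic AEs between an early visit (Days 21–27) and Day 28. These could include a related Grade 3 event that the pause rule would count. Over the assumed 28-day risks of 0.05 to 0.40, the most a single early visit costs is about 1 to 8 percentage points of risk. That is under half an expected subject in a group of 5, even if all five were seen on Day 21. These sizes rest on an assumed AE rate and a constant hazard; the window lengths come directly from the schedules.

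**What to change.** - In Section 5.1, define the unsolicited AE period as onset within 28 calendar days after each administration, in every group. Where the visit falls before Day 28, complete the remaining days at the next scheduled interim history (Visit 07, 12 or 17). Events with onset after Day 28 can be separated using the onset dates already listed.
- Alternatively, give Visits 06 and 11 in Schedules 3 and 4 the ±2 days already used for this milestone elsewhere. This still leaves a possible 2-day shortfall.
- Neither option equalises one dose and three. In Section 6.3.3, also summarise unsolicited AEs per administration, as is already planned for solicited AEs.

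**Cost.** The first option is one sentence and no extra visit, at the price of longer recall. The next visit is nominally 56 days after the dose, between Days 49 and 63 with ±7 days, so Days 22–28 would be recalled from 49 − 28 = 21 to 63 − 22 = 41 days back. The second option takes some scheduling flexibility from 10 subjects. The added summary is one more table.
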